# **OUTCOME**

- Fatal The study subject died.
- Not Recovered/Not Resolved The AE was ongoing at the time of death or at the time the subject was lost to follow up.
- Recovered/Resolved The AE resolved.
- Recovered/Resolved with Sequelae The AE is considered resolved; however, there is
  residual sequelae. Some events do not return to baseline, such as metastasis or
  progression of disease; however, once these events are determined by the Investigator to
  be stable or chronic, the Investigator may consider the event to be resolved or resolved
  with sequelae.
- Recovering/Resolving The AE is improving but is not yet completely recovered/resolved.
- Unknown The outcome of the AE cannot be determined.

MAR	Missing at random
MET	Metabolic equivalent task
MedDRA	Medical Dictionary for Regulatory Activities
MMRM	Mixed-effect model for repeated measures
mPAP	Mean pulmonary artery pressure
MVPA	Moderate to vigorous physical activity
NT-proBNP	N-terminal pro-brain natriuretic peptide
PEF	Peak expiratory flow
PFT	Pulmonary function test
PGA	Patient global assessment
PH	Pulmonary hypertension
PH-COPD	Pulmonary hypertension due to chronic obstructive pulmonary disease
PR	Electrocardiographic wave of P-R interval
PT	Preferred Term
PVR	Pulmonary vascular resistance
QID	4 times daily
QOL	Quality of life
QRS	Electrocardiographic wave of QRS interval
QT	Electrocardiographic wave of QT interval
RHC	Right heart catheterization
RVSP	Right ventricular systolic pressure

SAE	Serious adverse event
SAP	Statistical Analysis Plan
SGRQ	St. George's Respiratory Questionnaire
SOC	System Organ Class
SpO ₂	Saturation peripheral capillary oxygenation
TLC	Total lung capacity
UCSD SOBQ	University of California San Diego Shortness of Breath Questionnaire
WHO	World Health Organization

1 PREFACE

This plan provides further details of the planned analyses for Study RIN-PH-304 as presented in the study protocol. Based on the original Study Protocol RIN-PH-304 dated 12 January 2018 and the subsequent study protocol amendments (latest version study protocol Amendment 4 dated 20 October 2020), it provides further details of the planned analyses described in the study protocol, as well as any additional planned analyses. Additional post hoc or unplanned analyses that are not defined in this statistical analysis plan (SAP) may be performed. Such analyses will be documented in the clinical study report (CSR).

The RIN-PH-304 study is an adaptive study with a (fully blinded) decision for design modification based on enrollment and missing data metrics. This SAP pre-specifies analyses under the original design, as described in the study protocol (and associated amendments). To address the adaptive design feature of this study for a Contingent Parallel Design, as defined by the criteria in Section 10.2.1 of the study protocol, this SAP has been formally amended to provide analytic plans and details for the Contingent Parallel Design in Appendix 12.4.

[REDACTED]

- [REDACTED]
- [REDACTED]

- █ [REDACTED]
- █ [REDACTED]
- █ [REDACTED]
- █ [REDACTED]
- █ [REDACTED]

[REDACTED]

[REDACTED]

[REDACTED]

[REDACTED]

[REDACTED]

[REDACTED]

[REDACTED]

[REDACTED]

[REDACTED]

[REDACTED]

[REDACTED]

[REDACTED]

[REDACTED]

[REDACTED]

[REDACTED]

[REDACTED]

[REDACTED]

[REDACTED]

[REDACTED]

[REDACTED]

[REDACTED]

[REDACTED]

In light of the missing data arising from COVID-19, this SAP incorporates the ability to invoke a new definition for the primary endpoint based on a fully blinded assessment for missing data. This SAP defines the decision rules, data handling, and analyses for the updated definition of the

primary endpoint. In general, the amount of missing 6MWD data potentially due to the COVID-19 pandemic interfering with onsite measurements will define if adaptation is necessary. At the conclusion of the study, a blinded analysis will be performed to assess the extent of missing primary efficacy endpoint data (ie, 6MWD data). If the absence of 6MWD data, combined across subjects, treatment periods, and key visits (Baseline and Study Week 12) to be used for the final primary endpoint analysis would likely lead to an underpowered study or yield indeterminate results, an alternate primary endpoint will be used for the final primary endpoint analysis (see Section 9.2). This adaptation intends that the 6MWD is to be used as the primary efficacy endpoint for this study, except in the case where onsite measurements for the 6MWD are not available, and will occur regardless of Adaptation 1 (ie, for either the Original Crossover Design or the Contingent Parallel Design).

2 STUDY OBJECTIVES AND ENDPOINTS

2.1 OBJECTIVES

The primary objective of this study is to demonstrate the efficacy of inhaled treprostinil compared to placebo in improving exercise ability as measured by change from baseline in 6MWD following 12 weeks of active treatment in subjects with pulmonary hypertension due to chronic obstructive pulmonary disease (PH-COPD).

All secondary, safety, and exploratory objectives can be found in Section 2 of the study protocol.

2.2 PRIMARY ENDPOINT

The primary efficacy endpoint for this study is the change in 6MWD from Baseline to Week 12 in subjects with PH-COPD.

2.3 ALTERNATIVE PRIMARY ENDPOINT

An alternative primary efficacy endpoint of 6MWD/MVPA ranks will replace the change in 6MWD from Baseline to Week 12 if pre-specified rules (see Section 9.2 of this SAP for further details of the alternative primary endpoint and Section 9.3.1.2 for details regarding MVPA derivation).

2.4 SECONDARY EFFICACY ENDPOINTS

The secondary efficacy endpoints are the comparison for the effect of inhaled treprostinil versus placebo after 12 weeks of active treatment. Specifically:

- Change in MVPA as measured by actigraphy from Baseline to Week 12
- Change in overall activity as measured by actigraphy from Baseline to Week 12
- Change in Borg dyspnea score from Baseline to Week 12
- Change in 6MWD/Borg dyspnea composite score from Baseline to Week 12
- Change in quality of life (QOL) measured by the St. George's Respiratory Questionnaire (SGRQ) and the University of California San Diego Shortness of Breath Questionnaire (UCSD SOBQ) from Baseline to Week 12
- Change in plasma concentration of N-terminal pro-brain natriuretic peptide (NT-proBNP) levels from Baseline to Week 12
- Change in PGA from Baseline to Week 12.

2.5 SAFETY ENDPOINTS

The safety of inhaled treprostinil will be evaluated compared to placebo on the following parameters in comparison to placebo:

- AEs
- Clinical laboratory parameters
- Electrocardiograms (ECGs)
- Physical examination (PE) findings
- Oxygenation
 - Pulse oximetry (saturation of peripheral capillary oxygenation [SpO_2])
 - Supplemental oxygen requirement (L/min)
- Pulmonary function tests (PFTs)
 - Forced expiratory volume in 1 second (FEV1)
 - Forced vital capacity (FVC)
 - Total lung capacity (TLC)
 - Diffusion capacity of lung for carbon monoxide (DLCO)
- Vital sign measurements
- At-home spirometry.

2.6 EXPLORATORY ENDPOINTS

[REDACTED]

- [REDACTED]
- [REDACTED]
- [REDACTED]
- [REDACTED]
- [REDACTED]
- [REDACTED]
- [REDACTED]
- [REDACTED]
- [REDACTED]

[REDACTED]

[REDACTED]

[REDACTED]

[REDACTED]

3 STUDY DESIGN

3.1 GENERAL DESCRIPTION

This is a multicenter, randomized, double-blind, placebo-controlled, 34-week, crossover study of inhaled treprostinil (Tyvaso[®] [treprostinil] Inhalation Solution) in males and females 18 years or older diagnosed with WHO Group 3 pulmonary hypertension (PH) associated with chronic obstructive pulmonary disease (COPD). Subject eligibility will be based on the inclusion and exclusion criteria described in Section 4 of the protocol.

Approximately 136 eligible subjects will be randomized with half of the subjects receiving 12 weeks of active study drug (Period 1) then 12 weeks of placebo (Period 2) and the other half receiving 12 weeks of placebo (Period 1) then 12 weeks of active study drug (Period 2). Under the original study design, all randomized subjects will be treated with both active study drug and placebo.

The study will consist of the following periods:

Screening Period: At Screening Visit 1, prospective subjects (defined as having prior echocardiogram findings of right ventricular systolic pressure [RVSP] >40 mmHg and/or evidence of right ventricular hypertrophy or dysfunction), who sign the Informed Consent Form (ICF) will generally undergo all non-invasive screening assessments to evaluate eligibility, as listed in the inclusion/exclusion criteria. Potentially eligible subjects will undergo a right heart catheterization (RHC), including a vasodilator test and oxygen challenge, if possible, to confirm eligibility. If RHC results are available from a test performed within the previous 12 months (even if done without oxygen or vasodilator challenge), a repeat RHC during Screening Visit 1 is not needed. A window of up to 6 weeks is permitted to complete all assessments required for Screening Visit 1, including the start of low dose inhaled treprostinil. Prospective subjects meeting all eligibility criteria will be provided with and trained on inhalation of study drug using the Tyvaso Inhalation System and begin low dose (3 breaths QID) inhaled treprostinil for a minimum of 14 days (maximum of 18 days) to ensure tolerability and compliance. Subjects will be issued Sponsor-provided actigraphy, spirometry, and smart devices during Screening Visit 1 at the time of low dose inhaled treprostinil initiation for measurement of at-home activity and FEV₁/FVC. Subjects will be given training on the at-home use of these devices, as well as Instructions for Use. At Screening Visit 2, subjects will return to the study site following completion of low dose inhaled treprostinil exposure to undergo scheduled assessments and return unused study drug. Subjects who are intolerant of therapy (as determined by the Investigator), unable to follow the dosing regimen, or noncompliant with actigraphy, at-home spirometry, or smart device use during the Screening Period will be ineligible for randomization and deemed screen failures.

Washout Period - Washout 1: During Washout 1 (Study Week -1), prospective subjects will refrain from the use of inhaled treprostinil for a minimum of 7 days (maximum of 14 days) preceding entry into the Treatment Period 1 Baseline Visit (Study Week 1). Subjects will be contacted by telephone mid-week in Washout Period 1 to monitor safety.

Treatment Period 1: Eligible subjects approved by the Sponsor's Medical Monitor will undergo Treatment Period 1 Baseline Visit assessments (Study Week 1), be assigned to a treatment group based on the randomization schedule, and receive study drug. Target dosing with study drug (after titration) will be 12 breaths QID or to maximum tolerated dose. Two additional study visits to the study site will be conducted after the Treatment Period 1 Baseline Visit to complete study assessments (Study Weeks 6 and 12). Subjects will be contacted weekly by telephone during study drug titration (until 12 breaths QID or the maximum tolerated dose is achieved) and as needed thereafter to provide dosing instructions and to assess tolerance to study drug, AEs, and changes in concomitant medications.

Washout Period - Washout 2: Subjects will refrain from the use of study drug for a minimum of 7 days (maximum of 14 days) after the Treatment Period 1 Week 12 Visit (Study Week 12) and preceding entry into Treatment Period 2 (Study Week 14). Subjects will be contacted by telephone mid-week in Washout Period 2 to monitor safety.

Treatment Period 2: Subjects will undergo Treatment Period 2 Baseline Visit assessments (Study Week 14), be provided treatment based on the randomization schedule, and receive study drug for this period. Target dosing with study drug (after titration) will be 12 breaths QID or to the maximum tolerated dose. Two additional study visits to the study site (Study Weeks 19 and 25) will be conducted after the Treatment Period 2 Baseline Visit (Study Week 14) to complete study assessments. Subjects will be contacted weekly by telephone during study drug titration (until 12 breaths QID or the maximum tolerated dose is achieved) and as needed thereafter to provide dosing instructions and to assess tolerance to study drug, AEs, and changes in concomitant medications. At the completion of Treatment Period 2 (Study Week 25), subjects will be offered enrollment in the open-label extension study, RIN-PH-305.

4 SEQUENCE OF PLANNED ANALYSES

In brief, the specified primary endpoint for this study is 6MWD, which is a validated and reliable measure of exercise ability in patients with chronic respiratory diseases. Subjects perform the test at the clinical site following published guidelines and tests are conducted by trained personnel. For further details regarding the 6MWT and 6MWD, please see the study protocol.

The alternative primary endpoint for this study is a combined and standardized rank for 6MWD and MVPA, which is a measurement of subjects' time spent in moderate to vigorous activity during the course of daily living. The study protocol provides further detail about actigraphy and Section 9.3 of this SAP gives information about how blinded assessments will occur, the handling of data for actigraphy and MVPA, etc.

4.1 INTERIM ADAPTIVE ANALYSIS

Under the Original Crossover Design, at approximately 75% of subjects randomized, a blinded interim analysis will be performed to assess the extent of missing data for the primary analysis for the crossover design. The outcome of the analysis will inform a decision for the study to continue as the Original Crossover Design or switch to the Contingent Parallel Design as follows:

- If data presence $\geq 85\%$ for 6MWD or actigraphy data at the end of Treatment Period 2 (Study Week 25), the study will continue as planned under the Original Crossover Design.
- If data presence $< 85\%$ for both 6MWD and actigraphy data at the end of Treatment Period 2 (Study Week 25), the study will switch to the Contingent Parallel Design.

The goal of this assessment is to determine the amount of missing data due to subject dropout or otherwise lack of measurement (regardless of onsite or remote) and the outcome will be whether study continues to completion as the Original Crossover Design or the Contingent Parallel Design. Should there be a switch to the Contingent Parallel Design, the analysis plan described in Appendix 12.4 will be followed.

4.2 INTERIM EFFICACY ANALYSIS

A single interim efficacy analysis will be conducted when 75% of the subjects (ie, ~100 subjects) have completed the 26-week Treatment Period if both of the following criteria are met: a) the expected time to randomize the final (136th) subject is greater than 3 months; b) at least 90% of the 6MWD data is present for both Period 1: Baseline and Week 12 and Period 2: Baseline and Week 12 for these subjects. The projected time to randomize will be based on the average recruitment rate for the prior 6 months. This plan will allow early stopping for efficacy if recruitment is slow enough to warrant an interim review and if the data are sufficiently complete.

A non-binding futility analysis will also be conducted as part of the interim analysis. Analyses will be conducted for the primary endpoint of 6MWD per Section 9.1. Analyses will use the entire Full Analysis Population (FAS), including all available data for subjects who may be still ongoing in the study. The independent external statistical consultant will provide the results of these analyses to the independent Data Safety Monitoring Committee (DSMC) for their review and recommendation. The Sponsor will remain fully blinded throughout this process.

The DSMC Charter will contain more specific details regarding the processes for the interim analyses for efficacy and futility, such as timelines for data lock, information transfer and communications. However, the following approaches will be taken for projecting recruitment and the criteria for the interim analyses for efficacy.

4.2.1

[REDACTED]

[REDACTED]

4.2.2 Formal Criteria for Interim Efficacy Analyses

If conducted, the interim analysis will apply a 2-sided alpha level of 0.010 (75% information fraction), and at the final analysis at a 2-sided alpha of 0.022 with the overall Type I error rate at 2-sided alpha of 0.05. Efficacy boundaries for early stopping of the study for efficacy are based

¹ Subjects who were active in the treatment periods of this protocol as of 13 March 2020 will be assessed on a case-by-case basis by the Sponsor for inclusion of populations for adaptive, interim, and final analyses. All decisions will be documented and presented in the clinical study report.

on a Lan-DeMets spending function, with an O'Brien-Fleming boundary (GD-INFO; EAST[®], Cytel, Version 6.5). The corresponding non-binding futility boundary is provided as p-value less than or equal to 0.227 for the interim analysis (Lan-DeMets: O'Brien-Fleming).

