#### 10.3 ANALYSIS PLAN

Statistical analyses will be performed using 2-sided tests. A 0.05 significance level will be used in all tests of treatment differences. In addition, for labeling purposes only, the experiment-wise Type I error will be controlled to a maximum of 5%. A gatekeeper strategy may be employed such that any secondary endpoints or subset analyses will be considered for statistical significance only if the primary endpoint is statistically significant. The Type I family-wise error rate will be controlled at the 0.05 level of significance.

Data will be summarized by treatment group (and by visit when applicable). For parameters measured at baseline, the outcome variables of interest are the changes from baseline.

Summary statistics will include the mean, N, standard deviation, median, minimum, maximum, the 25th and 75th percentile values for continuous variables, and frequencies and percentages for categorical variables.

The SAP will specify the details of the models to be used for the efficacy, safety, and exploratory analyses. All statistical analyses will be performed by the Sponsor's biostatistics department personnel (or appropriate designees) using SAS®, Version 9.3 or higher or other validated software.

The Full Analysis Population will be defined as all subjects randomized into the study who receive at least 1 dose of study drug; all subjects will be counted in the group to which they were randomized, regardless of the study drug they were given. All efficacy analyses will be performed on this population, unless otherwise specified.

The Safety Population will be defined as all subjects enrolled into the study who receive at least 1 dose of study drug; all Safety Population subjects will be counted in the group corresponding to the study drug actually received, regardless of randomized assignment. All safety analyses will be performed on this Safety Population, unless otherwise specified.

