7 GENERAL CONSIDERATIONS FOR DATA ANALYSES

Given the crossover design utilized for this study, efficacy and safety summary tables will follow the general format that baseline and post-baseline data will be presented by the assigned treatment condition when those data are observed during the treatment period. Treatments will be labeled as “Treprostinil” and “Placebo” to correspond with the assigned treatment condition.

Any efficacy and safety data that are collected during the washout period between Periods 1 and 2 will be presented for the assigned treatment condition from Period 1. Any follow-up data collected after Period 2, while on this study, will be assigned to Period 2. Subjects who are not retained will not be replaced during the study.

For continuous variables, the summary statistics will include the mean, standard deviation, median, lower quartile, upper quartile, minimum, and maximum. Statistics will be expressed using the level of precision in which the variable was collected. For discrete variables, summaries will include the frequency and percent in each category. Whenever practical, categories of discrete variables will be ordered and labeled as they appear in the case report form (CRF), and all categories represented on the CRF will be included in summaries, even when they do not apply to any patients in the study.

For data collected on a fixed schedule, the nominal time point will be used for summarization. Evaluations from Unscheduled Visits are to be mapped to Scheduled Visits to the extent possible per the protocol-specified windows. Repeat or redundant observations within an assessment window and observations that do not fall within any predefined assessment window will be excluded from summaries. If an evaluation is repeated, such as to confirm an observed aberrant laboratory value, the analyses will use the later value if within the protocol-specified window.

Unless otherwise specified, all final statistical tests will be 2-sided at alpha level 0.05 if the interim analysis is not conducted, and 0.022, if conducted. All tables will be presented in landscape format. For practical reasons, the point size may be reduced to (but not less than) 7 point for tables that contain too much information to fit into a single page. SAS[®] version 9.4 or higher will be used. The Sponsor's Biostatistics Department will analyze the efficacy and safety data.

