7.7 MULTIPLE COMPARISONS AND MULTIPLICITY

A gatekeeper strategy will be employed to address multiple comparisons. Secondary endpoints will be formally tested only if the primary endpoint is statistically significant. If the primary analysis of treprostinil vs placebo change from Baseline to Week 12 is statistically significant at a 2-sided alpha level of 0.05, showing superiority of treprostinil over placebo, then the secondary endpoints will be formally tested.

[REDACTED]

- [REDACTED]
- [REDACTED]
- [REDACTED]
- [REDACTED]
- [REDACTED]

[REDACTED]

Other secondary endpoints, including change in QOL, based on the SGRQ and UCSD SOBQ, and PGA will not have formal statistical testing.

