12.4.2 Interim Efficacy Analysis

Section 4.2: A single interim efficacy analysis will be conducted when 75% of the subjects (ie, ~235 subjects) have completed the 12-week Treatment Period if both of the following criteria are met: a) the expected time to randomize the final (314th) subject is greater than 6 months; b) at least 90% of the 6MWD data is present for Period 1: Baseline and Week 12 for these subjects.

Section 4.2.1: Prior to any planned interim analysis being performed, the following steps will be followed to estimate the expected time to randomize the final (314th) subject:

[REDACTED]

Section 4.2.2: If conducted with exactly 75% information fraction, the interim analysis will apply a 2-sided alpha level of 0.019, and at the final analysis at a 2-sided alpha of 0.044 with the overall Type I error rate at 2-sided alpha of 0.05; the actual information fraction at the time of the interim analysis will be used to calculate the 2-sided alpha level that will be applied. Efficacy boundaries for early stopping of the study for efficacy are based on an O'Brien-Fleming spending function (PASS 12, NCSS, Version 12.0). There will be no corresponding futility boundary for the interim analysis.

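### The crossover interim and final levels in SAP 4.2.2 (labelled 2-sided 0.010 and 0.022) spend about 0.026, not the stated 2-sided 0.05, and disagree with the 0.019 and 0.044 in SAP 12.4.2

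*SAP*

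**What the plan says.** SAP 4.2.2 (crossover) says that the interim efficacy analysis, if conducted, will "apply a 2-sided alpha level of 0.010 (75% information fraction), and at the final analysis at a 2-sided alpha of 0.022". The same sentence puts the overall Type I error at 2-sided 0.05, and the next names a Lan-DeMets spending function with an O'Brien-Fleming boundary.

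SAP 12.4.2 (parallel design) also assumes 75% information, O'Brien-Fleming spending and overall 2-sided 0.05, but there "the interim analysis will apply a 2-sided alpha level of 0.019, and at the final analysis at a 2-sided alpha of 0.044". It adds that "the actual information fraction at the time of the interim analysis will be used to calculate the 2-sided alpha level that will be applied". The visible text of 4.2.2 has no such rule, although SAP 4.2 runs the interim on the full analysis population, "including all available data for subjects who may be still ongoing in the study".

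Two other SAP sections depend on these levels. Section 7 sets final tests as "2-sided at alpha level 0.05 if the interim analysis is not conducted, and 0.022, if conducted". Section 7.7 opens the secondary endpoints if the primary is "statistically significant at a 2-sided alpha level of 0.05" and does not mention an interim. The text that follows in 7.7 is redacted and may deal with this. Protocol 10.3 states: "Statistical analyses will be performed using 2-sided tests".

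**The concern.** Critical levels of this kind depend only on the spending function, the information fraction and the total alpha. They do not depend on whether the trial is crossover or parallel. SAP 4.2.2 and 12.4.2 share all three and print different pairs, so at least one pair is wrong. The pair in 4.2.2 also fails on its own terms: two tests at 0.010 and 0.022 cannot reach 0.05 even if their errors are simply added (0.032).

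These are the thresholds the DSMC and the final analysis would apply to the primary endpoint. After an interim, a final p between 0.022 and 0.044 would be declared a failure, and an interim p between 0.010 and 0.019 would not stop the trial, although the stated 0.05 allows both. If the discrepancy were noticed only after unblinding, choosing the level would be a post hoc decision on the primary result.

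**Working it through.** **Inputs.** Levels 0.010 and 0.022, information fraction t = 0.75, overall 2-sided 0.05, Lan-DeMets O'Brien-Fleming (SAP 4.2.2). Levels 0.019 and 0.044 (SAP 12.4.2). Effect 30 m, SD of differences 85 m, 124 evaluable (Protocol 10.2, SAP 5.1). Under the null the two test statistics are bivariate normal with correlation √0.75 = 0.866.

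**Step 1: the plan's own figure.** The 2-sided critical values are z = 2.576 (0.010) and z = 2.290 (0.022).

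P(|Z1| ≥ 2.576 or |Z2| ≥ 2.290) = 0.0256.

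The stated 0.05 is not reproduced. About 100 of 136 subjects is a fraction of 0.735, which gives 0.0258. For fractions from 0.70 to 0.85 the range is 0.0262 to 0.0241.

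**Step 2: what the named boundary gives.** With one-sided α = 0.025, the alpha spent by t is 2[1 − Φ(z_{α/2}/√t)].

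- Interim: z_{0.0125} = 2.241, and 2.241/0.866 = 2.588. The spend is 2[1 − Φ(2.588)] = 0.00965 one-sided, or z = 2.340.
- Final: solve P(Z1 ≥ 2.340 or Z2 ≥ c) = 0.025. This gives c = 2.012, one-sided 0.0221.
- Doubled: 2-sided 0.0193 and 0.0442.

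| Pair at t = 0.75 | Read as | Overall error |
|---|---|---|
| 0.010 / 0.022 (4.2.2) | 2-sided, as labelled | 0.0256 2-sided |
| 0.010 / 0.022 | one-sided | 0.0251 one-sided |
| 0.019 / 0.044 (12.4.2) | 2-sided | 0.0496 2-sided |
| 0.0193 / 0.0442 | 2-sided | 0.0500 2-sided |

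The one-sided halves, 0.00965 and 0.0221, round to the printed 0.010 and 0.022. A classical O'Brien-Fleming boundary does not rescue the label either: it gives 2-sided 0.0200 and 0.0439.

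**Step 3: consequence at the planned effect** (normal approximation, drift d√n/85, interim at 93 = 75% of 124).

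- Interim drift: 30√93/85 = 3.404. Chance of early success: Φ(3.404 − 2.576) = 79.6% as printed, against Φ(3.404 − 2.340) = 85.6%.
- Final drift: 30√124/85 = 3.930. Overall power over both looks: 95.2% as printed, against 97.4%.
- Observed difference needed, z × 85/√n: at the interim 22.7 m against 20.6 m; at the final 17.5 m against 15.4 m.
- With 100 subjects at the interim, as SAP 4.2 puts it, early success is 83.0% against 88.3%, and the thresholds are 21.9 m against 19.9 m.
- Sensitivity only: if the true effect were 20 m (an assumption; the placebo-corrected median Protocol 1.2.3 reports in PAH), overall power is about 64% against 74%.

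**Step 4: the level in Section 7.7.** If the primary were tested at 0.05 after an interim at 0.010, the formula of Step 1 with z = 2.576 and 1.960 gives 0.0516. With the interim corrected to 0.019 (z = 2.345) and 7.7 left at 0.05, it gives 0.055.

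**Step 5: dependence on the information fraction.** The same boundary gives 2-sided 0.0244 and 0.0429 at 80% information, and 0.0301 and 0.0414 at 85%.

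**The case against.** The strongest reply is that nothing is lost in error control. Protocol 10.3 caps the experiment-wise error at 5%, and 0.0256 respects that cap. Power at 30 m stays above the planned 90%, and the trial was sized at 2-sided 0.01, stricter than either final level. The interim is also conditional on slow recruitment and complete data. All of this stands: the error is conservative and its cost at the planned effect is modest. It does not make the statement in 4.2.2 true, and no visible text presents the lower levels as deliberate.

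Some narrower points also stand in part.

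- The 12.4.2 levels replace those in 4.2.2 only after a design switch, so the two interim levels are never in force together. The contradiction is first of all within 4.2.2, and 12.4.2 corroborates the expected values. The overlap is real for Section 7, however: 12.4.3 does not replace its 0.022 sentence, and 12.4 keeps unreplaced text, so under the parallel design 0.022 and 0.044 both apply.
- Section 7.7 is a gatekeeping sentence followed by a redaction, while 4.2.2 and 7 both give 0.022 explicitly. Testing at 0.05 after an interim would mean ignoring them. This is a matter of alignment.
- A Lan-DeMets function is designed to be recalculated at the actual fraction, and Protocol 10.4 also places formal criteria in the DSMC charter, which was not available. The missing rule in 4.2.2 is a lesser gap.
- The 20 m case comes from another population and should not drive the severity.

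**Conclusion.** The concern holds. As labelled, the levels in SAP 4.2.2 give an overall 2-sided error of 0.0256, about half of the stated 0.05, and no information fraction from 0.70 to 0.85 changes that. The boundary the section names gives 0.0193 and 0.0442 at 75% information, in agreement with SAP 12.4.2.

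That the printed pair is one-sided output labelled as 2-sided is an inference from the numerical match. The inconsistency does not depend on it. The power figures assume 30 m, SD 85 m, 124 evaluable subjects and an interim at exactly 75% of them.

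The Type I error is not inflated unless the primary is tested at an unadjusted 0.05 after an interim, as a literal reading of the visible text of 7.7 would allow. This should be fixed: it is a primary decision threshold that is wrong as written, with conservative effect, and it applies only if an interim efficacy analysis is run.

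**What to change.** Before any unblinded look:

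1. In SAP 4.2.2, either (a) state 2-sided 0.019 and 0.044 at exactly 75% information with overall 2-sided 0.05, or (b) relabel 0.010 and 0.022 as one-sided with overall one-sided 0.025. Option (a) is simpler. Option (b) also needs changes in SAP 7 and Protocol 10.3, which specify 2-sided tests. If the sponsor did intend 2-sided 0.010 and 0.022, the stated overall error should become about 0.026 and the boundary description should change to match.
2. Add to 4.2.2 the rule already in 12.4.2, that the actual information fraction sets the levels.
3. In Sections 7 and 7.7, replace the fixed 0.022 and the unadjusted 0.05 with the final alpha in force under Section 4.2.2: 0.05 if no interim is run, about 0.044 2-sided if it is run at 75% information. Because 12.4.3 leaves the Section 7 sentence standing, word it to cover the parallel design too. Correcting 4.2.2 without 7.7 would leave the 0.055 of Step 4 open.
4. Check that the DSMC charter carries the same levels.

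The cost is SAP wording under option (a), with no new data or patients. It restores about half of the stated alpha without exceeding 0.05.
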